#### Safety population

By default, patients who underwent the procedure after randomization will be included in the safety population and assigned to the glue obliteration arm. Patients who underwent the early-TIPS procedure without regard for its successful completion will be included in the safety population and assigned to the early-TIPS arm. Patients who, for any reason, could not undergo either procedure will be excluded from the safety population.

## **Section 5: Trial Population**

## **5.1 Eligibility**

**Inclusion criteria:** 

- Age  $\geq$  18 and  $\leq$  75 years.
- Cirrhotic patients with variceal bleeding from gastroesophageal gastric varices type 2 or isolated gastric varices type 1 or 2 (Sarin classification) according to the following criteria: endoscopic signs of an active spurting or oozing from gastric varices (GV); adherent blood clots, white nipple signs, or erosions on the GV and absence of other bleeding sources. Cirrhosis: The diagnosis of liver cirrhosis is based on previous liver biopsy or on the combination of clinical, biochemical, and radiological findings. If biopsy findings are unavailable and in case of non-complicated cirrhosis, non-invasive markers will be used.
- Hemodynamically stable patient without clinically significant rebleeding (Baveno criteria) within 12 hours after the initial endoscopy with glue obliteration.
- Written informed consent obtained.
- Patient affiliated to a social security system.

#### **Exclusion criteria:**

- Pregnant woman or breastfeeding.
- Minor and patients older than 75 years.
- Hepatocellular carcinoma outside the Milan criteria or other cancer at a palliative stage.
- Non cirrhotic portal hypertension.
- Child Pugh score > 13.
- History of severe or refractory hepatic encephalopathy unrelated to gastrointestinal bleeding.
- Congestive heart failure.
- History or presence of pulmonary hypertension.
- Patient with other indication for TIPS.
- Uncontrolled gastric variceal bleeding.
- Portal vein cavernoma.
- Patient who have previously received a TIPS procedure.
- Failure to receive clear information in patients without an identified trusted person.
- Refusal of the participation agreement by signing the information form and consent as defined.
- Exclusion period from another biomedical study

A list of ineligible cirrhotic patients and the reasons for their ineligibility was created in each participating center. This list will allow us to document the representativeness of the study sample.

## 5.2 Withdrawal/Follow-up

Criteria for stopping the study are:

- withdrawal of consent,
- liver transplantation,
- loss to follow up,
- enrollment of ineligible subjects.

Patients withdrawn from the study for withdrawal of consent, liver transplantation or loss to follow up will be censored at the date of withdrawal. Ineligible subjects will be excluded from the mITT analyses. Unless consent to analyze data is also withdrawn, all the data collected prior to withdrawal from the study will be considered for analysis.

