#### 6.4 Harms

Safety analyses will be conducted in the safety population using the same evaluation period as for efficacy analyses (i.e. from randomization until end of 12-month follow-up).

The number of adverse events and SAE observed in each strategy group will be described and compared by using Chi-squared test or Fisher's exact test, as appropriate. Adverse events will be described in a table in order of decreasing frequency.

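### Section 5.2 makes discovered ineligibility a reason for stopping the study; read as written, this cuts short the 12-month safety window the SAP sets for treated patients

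*SAP*

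**What the plan says.** Section 5.2 (Withdrawal/Follow-up) opens a list with "Criteria for stopping the study are". Its fourth item is "enrollment of ineligible subjects". The section then gives three rules:

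- For the other three reasons: "Patients withdrawn from the study for withdrawal of consent, liver transplantation or loss to follow up will be censored at the date of withdrawal".
- For the fourth: "Ineligible subjects will be excluded from the mITT analyses".
- For everyone, unless consent to analysis is also withdrawn: "all the data collected prior to withdrawal from the study will be considered for analysis".

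Three other places bear on the same patients:

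- **Section 3.1 (Trial Design)** says that randomized patients are followed to the end of the 12-month period and makes no exception for ineligibility.
- **Section 4.3 (Safety population)** says "Patients who underwent the early-TIPS procedure without regard for its successful completion will be included in the safety population". Its only stated exclusion is for patients who could undergo neither procedure.
- **Section 6.4 (Harms)** sets the evaluation period as "from randomization until end of 12-month follow-up".

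**The concern.** Removing a patient from an efficacy set and ending that patient's observation are different acts. Section 5.2 puts ineligibility in the list that governs the second. The other three items in the list apply to individual patients, so this one does too.

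A site that follows section 5.2 literally would cease collecting data on a treated patient once an eligibility error comes to light. Sections 3.1, 4.3 and 6.4 expect that same patient to supply 12 months of safety data.

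What is at stake is the completeness of the harm data, not the primary comparison. An analysis set can be redefined after the fact, but adverse events that nobody recorded cannot be recovered by a sensitivity analysis.

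**Working it through.** The SAP gives no figure on this point, so there is none to reproduce. The check is mainly a comparison of sections.

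**1. Can ineligibility surface after treatment?** Yes. Section 4.3 provides for randomized patients later found not to meet inclusion criteria, in both the mITT and per-protocol definitions. Section 3.1 places TIPS as early as possible after randomization and before Day 4, so the device may already be in place.

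**2. Does such a patient stay in the safety population?** Yes. Membership depends on having undergone a procedure. Eligibility is not a condition in either arm.

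**3. What window applies?** Section 6.4 says randomization to 12 months. Section 5.2, taken literally, says randomization to the date of discovery. For discovery on day d, the unobserved share of the window is (365 − d)/365. Two of the SAP's own time points illustrate it:

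- d = 42: (365 − 42)/365 = 323/365 = 88%
- d = 180: (365 − 180)/365 = 185/365 = 51%

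**4. Does the analysis allow for unequal observation?** No. Section 6.4 compares adverse events by Chi-squared or Fisher's exact test, and section 6.2 reports TIPS and glue complications as frequencies in the safety population. Neither uses person-time or censoring. The time-to-event analyses in section 6.2 do censor, but they run on the mITT and per-protocol sets, which leave these patients out.

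**5. Which harms are most exposed?** Comparing the exclusion criteria (section 5.1) with the TIPS complications (section 6.1):

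| Exclusion criterion | Listed TIPS complication |
|---|---|
| Congestive heart failure | Heart failure |
| History of severe or refractory encephalopathy unrelated to gastrointestinal bleeding | Encephalopathy |

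For these two, follow-up would stop in patients whom the plan's own criteria single out for the harm being counted.

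**6. What does one missed case do?** With the planned 52 per arm (section 3.3), 1/52 = 0.019, or 1.9 percentage points. The early-TIPS safety group may differ from 52, since it depends on who underwent the procedure.

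**The case against.** The strongest reply is that the SAP nowhere says safety observation ends for these patients. That is inferred from the heading of the list in section 5.2. The section also separates the groups: three reasons lead to censoring at withdrawal, while ineligible subjects are given an analysis-set consequence. Conduct of follow-up normally belongs to the protocol, which is not at hand and may provide for continued safety visits. Under section 3.2, only patients who meet the criteria on eCRF data can be randomized, which should keep such cases rare.

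Much of this stands, and it makes the point conditional. It does not remove it. Ineligibility is expressly listed as a criterion for stopping the study, and that is a stated rule in conflict with sections 3.1 and 6.4, not a detail left to the protocol. If the protocol does continue observation, section 5.2 is misworded and still needs correcting.

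A reader might infer several stronger things that the document does not support:

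- **That only data from before withdrawal may be used.** The sentence says such data will be considered. It contains no restriction to them.
- **That the absence of a censoring date for ineligible subjects is itself a safety gap.** That date serves the time-to-event analyses, and patients excluded from the mITT set need none there.
- **That "History or presence of pulmonary hypertension" is a further example of the overlap.** It is an exclusion criterion but not a listed TIPS complication. The overlap is clear for two conditions only.
- **That the SAP scores unobserved harms as absent.** Section 6.3 leaves missing values missing. The undercount is a side effect of crude frequencies, and it also arises with consent withdrawal, transplantation and loss to follow-up, in either arm.

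**Conclusion.** The point holds in a limited, conditional form. Section 5.2 conflicts with sections 3.1, 4.3 and 6.4 on how long a treated patient found ineligible is observed. If sites follow section 5.2 literally, harms are truncated in patients who remain in the safety denominator, and the reported complication frequencies could be too low.

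The size cannot be derived from the SAP, which gives neither an expected number of ineligible patients nor expected complication counts. It is tempting to assume 3–5% ineligible among 104 and a true count of 3–4 complications, and to conclude that one missed case understates a rate by 25–33%. Neither input is in the document. A loss also requires ineligibility on a relevant criterion, discovery after the procedure, a complication after discovery, and no continued observation. The one supportable figure is 1.9 points per missed case in an arm of 52, and the total effect is probably small.

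The direction is clearer for the TIPS complication frequencies, which can only be lowered by missed cases. For the between-arm comparison of adverse events it is uncertain, because truncation can occur in both arms.

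**What to change.** Reconcile sections 3.1, 4.3, 5.2 and 6.4:

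1. Delete ineligibility from the stopping criteria in section 5.2, so that its only consequence is the exclusion from the mITT and per-protocol sets already stated.
2. State that randomized patients found ineligible remain under observation to Day 365 for death, rebleeding and adverse events, unless consent is withdrawn or absent.
3. State that those who underwent a procedure are kept in the safety analyses for the full window of section 6.4, and flag them in the harms table.
4. If follow-up has already ended for some of them, report their number, arm and observed time.

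This concerns data collection and reporting only, not treatment. The cost is a few lines of SAP text, the remaining scheduled visits for a few patients, and a matching protocol line if the protocol does not already provide for this.

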## **5.3 Baseline Patient Characteristics**

The description and initial comparison of randomized groups will focus on:

- Patient information: demographic characteristics, clinical exams, place of support, medical history, radiological exams, diagnosis of cirrhosis, cause and complications of cirrhosis, hepatocellular carcinoma, and concomitant treatments
- Endoscopic characteristics of initial bleeding: endoscopic condition, lesion responsible for bleeding, pre-existing treatment
- Biological results at admission: virology, hematology, blood biochemistry, arterial blood gas, bacteriology, ascites puncture, plasma
- Scores: Child-Pugh, MELD, MADDREY

Quantitative variables will be in the form of a table showing the number of values and the number of missing data, the mean and median, standard deviation, coefficient of variation, the minimum and maximum for each group and for the overall population.

Categorical variables will be in the form of a table revealing the number of values and the number of missing data, the percentage of each category and the confidence intervals for each group and for the overall population.

Continuous variables will be compared using Student's t-test or the Mann-Whitney test, as appropriate. Categorical variables will be compared using the Chi-squared test or Fisher's exact test, as appropriate.

## **Section 6: Analysis**

#### 6.1 Outcome Definition

## Primary endpoint

Death (all cause) or clinically significant rebleeding (upper gastrointestinal bleeding whatever its origin, with event date) during the one-year follow-up.

#### **Secondary endpoints**

- 1- Survival at Days 42, 90, 180 and 365.
- 2- Incidence of liver related death at Days 42, 90, 180 and 365.
- 3- Incidence of significant rebleeding at Days 42, 90, 180 and 365.
- 4- Cumulative number of packed red blood cells required by each treatment arms.
- 5- Incidence of complications of cirrhosis during the 12-month follow-up.
- any of the complication below
- bacterial infections,
- jaundice,
- ascites.
- spontaneous bacterial peritonitis,
- hepatic encephalopathy,
- hepatorenal syndrome,
- further decompensation.
- 6- Frequency of:
- TIPS technical failure and TIPS complications: thrombosis, heart failure, infection and encephalopathy.

- Technical failure of GO and complications of GO: migration of glue, infection of the site of injection, significant bleeding during the procedure (hospital stay, blood transfusion, 3 g drop in hemoglobin).
- 7- Number of patients lost to follow up at Day 365 in each group
- 8- Change of MELD score between inclusion and Day 180 in each group.
- 9- Number of days spent in hospital in each group during the 12-months follow-up.
- 10- Number of bacterial infections and localizations.

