#### Describe:

- 6/ TIPS and glue obliteration complications.
- 7/ Compliance in each group.
- 8/ The evolution of liver function at 6 months in each group.
- 9/ The need for hospitalization in each group during follow-up.
- 10/ Describe the number of infections and their localizations.

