#### *Incidence of rebleeding during follow-up*

The association of study arms with rebleeding hazard function will be tested using univariate and multivariate Cox models. The cumulative risk of rebleeding during follow-up in each arm will be estimated by calculating the cumulative incidence function (CIF) rebleeding at 12 months. In this approach, death free of rebleeding during follow-up will be considered as a competing event.

Incidence of the other complications of liver cirrhosis during follow-up

The association of treatment group with the hazard function of other complications will be tested using univariate and multivariate Cox models. The cumulative risk of other complications during follow-up in each arm will be estimated by calculating the CIF at 12 months. In this approach, death free of complications during follow-up will be considered as a competing event.

Cumulative number of packed red blood cells required by each treatment arms.

Variation of MELD score between inclusion and 6 months in each arm

Number of days that patients spend in hospital during follow-up

Comparison between strategy groups will be performed with Student's t-test or the Mann-Whitney test, as appropriate.

Frequency of TIPS technical failure and TIPS complications: thrombosis, heart failure, infection and encephalopathy. Frequency of technical failure of GO and complications of GO: migration of glue, infection of the site of injection, significant bleeding during the procedure (hospital stay, blood transfusion, 3 g drop in hemoglobin).

This analysis will be performed on the safety population.

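### Endpoint 6 defines procedural bleeding for glue obliteration only, so the two procedures are not described like for like on that harm

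*SAP*

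**What the plan says.** Among the objectives to be described, section 2 of the SAP lists "TIPS and glue obliteration complications". Endpoint 6 in section 6.1 answers it with one list per procedure.

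- TIPS: "TIPS technical failure and TIPS complications: thrombosis, heart failure, infection and encephalopathy".
- Glue obliteration: technical failure, then migration of glue, infection at the injection site and "significant bleeding during the procedure (hospital stay, blood transfusion, 3 g drop in hemoglobin").

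Section 6.2 repeats both lists unchanged, opening with "Frequency of TIPS technical failure and TIPS complications: thrombosis, heart failure, infection and encephalopathy". Its only instruction for them is "This analysis will be performed on the safety population". It names no test between the arms and no composite of the listed items.

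Three other parts of the SAP touch on bleeding. The primary endpoint counts clinically significant "upper gastrointestinal bleeding whatever its origin, with event date". Secondary endpoint 4 totals packed red cells by arm. Section 6.4 says "The number of adverse events and SAE observed in each strategy group will be described and compared by using Chi-squared test or Fisher's exact test", over the whole period from randomization to month 12.

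**The concern.** The SAP writes criteria for significant procedural bleeding and then applies them to one of the two procedures. Neither list is marked as open to other complications, and the same wording stands in the endpoint definition and in the analysis section, so an analyst who follows the text would not tabulate procedural bleeding for TIPS.

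A reader of the trial report would then see a bleeding frequency for glue, no corresponding line for TIPS, and no way to tell whether the absence means that none occurred or that none was counted. Describing the complications of both procedures is a stated objective, and the trial is open label, so it is better to settle what counts as a complication in advance than to leave it to judgement at reporting.

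**Working it through.** The point rests on the text. No stated figure in the SAP depends on it, so there is none to reproduce.

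**Step 1. The two lists side by side (section 6.1, endpoint 6; same in section 6.2).**

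| Item | TIPS | Glue |
|---|---|---|
| Technical failure | listed | listed |
| Procedural bleeding, with criteria | absent | listed |
| Infection | listed, unrestricted | injection site only |
| Heart failure | listed | absent |
| Encephalopathy | listed | absent |
| Thrombosis | listed | absent |
| Glue migration | not applicable | listed |

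Bleeding is missing on the TIPS side. On heart failure, encephalopathy and infection the TIPS list is the broader one.

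**Step 2. Does another outcome supply the missing frequency?**

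- *Primary endpoint and rebleeding endpoint.* The primary endpoint requires upper gastrointestinal bleeding, and the section 6.1 definition of significant rebleeding requires melena or hematemesis. A TIPS bleed that presents in this way and meets the criteria is counted, but as rebleeding and not as a complication of the procedure. One that does not present in this way is not counted. A fatal bleed is a primary event as a death.
- *Packed red cells.* Counted in both arms, but not attributed to a procedure.
- *Section 6.4.* Not limited to the endpoint 6 lists, so a TIPS bleed reported as an adverse event appears there. The section gives no definition of procedural bleeding and does not feed endpoint 6.

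By contrast, encephalopathy is collected in both arms under endpoint 5, and bacterial infection under endpoints 5 and 10. Procedural bleeding has no such two-arm counterpart with defined criteria.

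**Step 3. How likely is it that the gap matters?** The SAP gives no rate, so the rate r below is an assumption. With the 52 patients per group of section 3.3 used as a round number of TIPS procedures, the expected count is 52 × r and the chance of at least one event is 1 − (1 − r)^52.

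| Assumed r | Expected events | Chance of at least one |
|---|---|---|
| 1% | 0.5 | 41% |
| 2% | 1.0 | 65% |
| 5% | 2.6 | 93% |
| 10% | 5.2 | over 99% |

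This is an illustration only. The actual denominator is the safety population, which section 4.3 defines by the procedure undergone.

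**Step 4. The glue criteria themselves.** Endpoint 6 puts three criteria in a parenthesis without saying whether one or all are needed. The definition of significant rebleeding in section 6.1 says explicitly that any one suffices. Endpoint 6 also uses a hospital stay where that definition uses an admission. A patient still in hospital at the early endoscopic control (day 5 to day 8, section 3.1) could meet the stay criterion without the bleed having had any consequence. The SAP does not say how many patients would still be in hospital then, and the later sessions at days 42 to 365 may differ.

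**The case against.** The strongest reply is that these are procedure-specific, descriptive lists. They need not match, no test between the arms is planned for them, and a TIPS bleed can still surface in the adverse event tables, the transfusion totals or, if it is an upper gastrointestinal bleed, the primary endpoint. The protocol is not at hand and may define procedural complications more fully. All of this stands, and it limits the point to one of reporting. It does not remove the point, because none of those places gives a defined frequency of procedural bleeding for TIPS, and the SAP itself chose to write such a definition for the other procedure.

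Three stronger readings are tempting and are not supported.

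- *That the complication frequencies understate TIPS harm overall.* The lists differ in both directions (Step 1), so the net direction cannot be read from the SAP.
- *That each missed bleed lowers the TIPS complication rate by 1/52 = 1.9 percentage points.* Endpoint 6 defines no overall complication rate. Endpoint 5 adds an any-complication item and endpoint 6 does not. An unlisted bleed does not change the frequency of thrombosis or heart failure, and 52 is the planned number per group rather than the safety denominator.
- *That bleeding from TIPS goes mostly to sites that the primary endpoint cannot see.* The SAP says nothing about where such bleeding occurs or how often. The argument needs only the wording of the endpoint definitions.

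**Conclusion.** The point holds as an asymmetry in one descriptive safety endpoint. Endpoint 6 applies a defined procedural-bleeding item to glue obliteration only, so the TIPS complications it reports omit significant procedural bleeding, and the two procedures are not described like for like on that harm. The size of the omission and the net direction across all complications cannot be determined from the SAP. The primary analysis and the planned tests are unaffected, and events reported as adverse events remain visible under section 6.4.

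The conclusion assumes that the lists are applied as written, with no fuller definition of TIPS complications elsewhere. It is worth correcting because the change is small and removes an avoidable ambiguity from a stated objective.

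**What to change.** In section 6.1 (endpoint 6) and in the matching paragraph of section 6.2:

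1. Add significant bleeding during or after the procedure to the TIPS list, with the same criteria as for glue. Identify cases from adverse event and transfusion data, and report them in the safety population.
2. State the time window and use the same one for both procedures, so that the correction does not create a new asymmetry. If the window extends beyond the procedure, say that an event may also count as rebleeding.
3. For both procedures, state that any one criterion suffices.
4. For both procedures, replace the bare hospital-stay criterion with admission or prolonged stay because of the bleeding.

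The cost is SAP wording and slightly more analysis work, with some case review to attribute bleeds to a procedure. The reported TIPS complication profile may become less favourable.
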